8.3 Handling of Missing Data

Every effort will be made to collect all data at each time point in the study. The PI and the Clinical Data Monitor will minimize the amount of missing data by appropriate management of the prospective clinical trial, proper screening of subjects, and training of clinicians. If a subject misses a dietary entry in to either the paper or electronic diary, a look back entry for that value is allowed provide for the week preceding the event. Outside this window, data will be considered missing. All partial data available for subjects who drop out during the course of the study will be included.

Missing data will only be imputed for the co-primary endpoints. The LOCF method will be utilized at the 3 month time point for the two co-primary endpoints of percent change from baseline in appetite suppression scores and %TBWL. The ANCOVA analysis with LOCF on the mITT population for the co-primary endpoints were planned for the main analyses for the study to determine study success. Note, however, by definition, the mITT population may not need LOCF as only those with a week 12 visit will be included in the mITT population. A patient, however, may have had a week 12 visit but have missing data on some or all co-primary endpoints, in which case LOCF methods will be used.

To assess the potential effect of missing data on the co-primary effectiveness endpoints, a tipping point analysis will be computed for each co-primary endpoint on the mITT population. If none of the 5 co-primary endpoints are missing at week 12, the tipping point analysis will be a moot point and will not be conducted. A tipping point analysis involves imputing each missing data point, one-at-a-time until the study conclusion is tipped in the other direction (i.e., from statistically significant to non-statistically significant or vice versa, from non-statistically significant to statistically significant).8.4 Subject Population for Safety and Effectiveness Analysis

Safety analyses will be conducted an Intent to Treat (ITT) basis (i.e. all subjects who were enrolled). Primary and Secondary effectiveness analyses will be performed on a modified intent-to-treat basis (MITT; i.e. all subjects who initiated therapy, defined as subjects who initiated their first Treatment Period Visit) as will all per subject effectiveness analyses (e.g. responder analyses). Primary and Secondary endpoints (e.g. weight loss, appetite) will also be conducted on a completer, or per protocol basis (defined as those subjects that completed all visits in the study).

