8. STATISTICAL CONSIDERATIONS AND ANALYSIS PLAN

8.1.1 General Methods

Categorical variables will be summarized by number and percent. Continuous variables will be summarized by total number (N), mean, standard deviation (SD), median, minimum and maximum. Ninety-five percent, 2-sided confidence intervals will be reported, as appropriate.

As this was a randomized trial, the groups are expected to be balanced on demographic and baseline characteristics. No formal testing for this is planned.

Planned analyses and summaries for the primary safety endpoint, co-primary efficacy endpoints, secondary efficacy endpoints and exploratory efficacy endpoints are detailed below.

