8.2 Justification of Sample Size

As per the protocol, the calculation sample size for the study is based on conservative imputation of results from other studies on weight loss including the use of TENS for weight loss. The degree of coaching/dietary support throughout the present study is moderate intensity lifestyle/weight coaching. The sample size modeling assumes an average of 3.5% TBWL in Control Subjects using diet and exercise alone. The estimated weight loss in Treatment Subjects is modeled from preliminary data on T6/T7 dermatomal TENS when used for

weight loss: 6% TBWL. The variance of the responses in the study (i.e. Standard Deviation) was modeled at +/- 5% TBWL. This value was taken from previous dermatomal TENS weight loss study results. The model assumes a 30% drop out rate across groups and an 80% powered endpoint using an adaptive p spending model wherein interim posterior probability assessments are allowed after enrolling proscribe cohorts of not less than 67% of subjects. The alpha penalty will be minimized per interim by assessing the relationship between stimulation (i.e. dose) and weight loss using Normalized Linear Dynamic Modeling (NLDM) to determine overall sample size projected (i.e. futility) rather than assessing the primary hypothesis per se. Monotonicity will not be assumed in this analysis. This modeling provides an estimate of 80 subjects per group, for a total study size of 160 subjects. However, the protocol allows for enrollment of additional subjects should the interim model project under powering of the primary endpoint.

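### The deciding analysis (ANCOVA with LOCF on mITT) handles dropout poorly under either of two conflicting mITT definitions, and the tipping point remedies neither

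*Combined protocol and SAP*

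**What the plan says.** Section 8.1.4 makes ANCOVA with LOCF on the mITT population the analysis that decides success. One significant result among %TBWL and the four appetite scores is enough. Section 8.3 sets the imputation rule: "The LOCF method will be utilized at the 3 month time point for the two co-primary endpoints". The SAP text in the Protocol Summary repeats both.

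The mITT population is defined in two ways:
- **Section 8.1.2**, and the SAP text in the Protocol Summary, require that a subject started therapy and has data through week 12. Section 8.3 relies on this when it remarks that LOCF may hardly be needed.
- **Section 8.4** takes "all subjects who initiated therapy, defined as subjects who initiated their first Treatment Period Visit", with no condition on week 12.

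Section 8.3 also says that dropouts' partial data will be used, without saying in which analysis. The sensitivity analysis named for missing data is a tipping point on mITT, described as "imputing each missing data point, one-at-a-time until the study conclusion is tipped in the other direction". It is cancelled if no co-primary value is missing at week 12. On expected dropout, section 8.2 says: "The model assumes a 30% drop out rate across groups". It gives no time frame.

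**The concern.** Both definitions leave dropout poorly handled, in different ways. If week-12 data are required, the deciding comparison is between those who stayed, and randomisation no longer protects it. If they are not required, a subject who leaves early has the last recorded value treated as the week-12 result. Where weight is still falling, that understates the loss the subject would have shown if retained, and how much each arm is affected depends on how many leave it and when.

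Unequal dropout is plausible here. The trial is open label (section 5.3), Control subjects receive neither device nor app (section 5), and stopping for severe skin irritation (Protocol Summary, Visit Schedule) arises only in Treatment. A sensitivity analysis should show whether the conclusion survives unfavourable assumptions about those who left. The tipping point either omits them or is too loosely described to be carried out in one way.

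**Working it through.** **1. The plan's own figure.** Inputs from section 8.2 are Control "assumes an average of 3.5% TBWL in Control Subjects using diet and exercise alone", Treatment "weight loss: 6% TBWL", SD 5 and "80% powered endpoint using an adaptive p spending model". No test alpha is stated. I assume 0.05 two-sided, in line with section 8.1.1 ("Ninety-five percent, 2-sided confidence intervals will be reported, as appropriate").

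n per arm = 2 × (1.96 + 0.842)² × 5² / 2.5² = 62.8, so 63. Inflating by 30% as 63 × 1.3 gives 82, close to the stated 80 per group. Dividing by 0.7 gives 90. How dropout was inflated is a separate point; below I use 80 per arm, a difference of 2.5 and 30% dropout.

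**2. The two definitions side by side.**

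| | Section 8.1.2 | Section 8.4 |
|---|---|---|
| Dropouts before week 12 | Outside mITT | Inside mITT |
| What LOCF fills | Gaps among week-12 attenders | Those gaps plus every such dropout |
| Tipping point | Never reaches dropouts | Reaches them, but with no values, order, arm or shift range |
| If all 30% leave before week 12 | 80 × 0.7 = 56 per arm analysed; power 75.4% (normal approximation) | 80 × 0.3 = 24 values per arm carried forward, 48 of 160 |

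Even under section 8.1.2, LOCF may matter for appetite. Section 9.8 places a diary day after the week-12 visit, so a subject who attends and then leaves can lack it. Section 8.1.4 instead describes weekly diaries.

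**3. Size of the LOCF effect on weight, section 8.4 only.** Assumptions not in the documents: loss is linear to week 12, dropouts' last visits fall equally at weeks 1, 4 and 8, and dropout is unrelated to outcome. The mean fraction of the week-12 loss reached at the last visit is (1/12 + 4/12 + 8/12)/3 = 0.361. With dropout proportions dT and dC:

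LOCF difference = 6 × (1 − 0.639 dT) − 3.5 × (1 − 0.639 dC)

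| Dropout by week 12, Treatment/Control | Calculation | LOCF difference (target 2.50) |
|---|---|---|
| 30%/30% | 2.5 × (1 − 0.192) | 2.02 (19% smaller) |
| 16.3%/16.3% | 2.5 × (1 − 0.104) | 2.24 (10% smaller) |
| 20%/40% | 5.233 − 2.606 | 2.63 |
| 40%/20% | 4.467 − 3.053 | 1.41 |

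The second row reads 30% as dropout over the full 24 weeks at a constant rate, so dropout by week 12 is 1 − √0.7 = 16.3%.

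**4. False success.** A simulation used the same assumptions, each dropout's last value scaled in proportion to time, 80 per arm, 5,000 runs and a t-test without covariate.
- With no true difference (3.5% loss in both arms), type I error is about 4–5% at 30%/30%, 5% at 25%/35% (bias +0.22), 9% at 20%/40% (bias +0.44) and 24% at 10%/50% (bias +0.89).
- With a true difference of 2.5 and 30%/30% dropout, power is 79% with LOCF and 73% for completers. At 40%/20%, LOCF power is 48%.

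**The case against.** **The week-12 definition is the better-attested one.** It appears in section 8.1.2 and in the Protocol Summary's SAP text, and section 8.3 relies on it. Only section 8.4 departs from it, and the SAP text has no counterpart to that section. On this reading none of the estimates in step 3 applies. That stands. The defect then is that dropouts are left out of the deciding analysis and out of its sensitivity check.

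**A reader might infer that LOCF will fill up to 30% of week-12 values.** The documents do not support this as a ceiling or as a week-12 rate. It needs section 8.4, and 30% is a planning figure without a time frame in a study that runs to week 24.

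**A reader might also infer that the tipping point cannot test dropout at all.** That is strictly true only under section 8.1.2. Under section 8.4, dropouts' missing values do enter it; the fault there is lack of specification.

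**At equal dropout the harm is modest.** The effect is diluted and type I error is not inflated. LOCF even had more power than completers in the simulation, where carried-forward values also have smaller spread by assumption. That stands, and a general claim that LOCF produces false success or wrong standard errors would go beyond what has been shown.

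**The inputs are partly assumed.** Section 8.2 gives mean losses but no trajectory, and the unequal splits are illustrations. Taking 2.50 as the target supposes that dropouts would have continued like those retained; the plan states no estimand. The sums cover weight, not the four appetite scores.

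**Other provisions exist.** These are a per-protocol analysis, a repeated-measures ANOVA of raw appetite scores, maximum likelihood for censoring (section 5) and multiple imputation for the interim analyses (Protocol Summary). None is tied to the final co-primary ANCOVA.

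**Conclusion.** The point holds in conditional form. The mITT definitions conflict, and the deciding analysis is weak under each. Under section 8.1.2, early dropouts are excluded and untested. Under section 8.4, they are carried forward and then examined by a procedure that two analysts could run differently on the same data.

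For weight under section 8.4, LOCF turns a difference of 2.50 into roughly 2.0 to 2.2 when dropout is equal, depending on whether the planned 30% falls before week 12 or is spread over 24 weeks. Unequal dropout can push the estimate either way, to 2.63 or 1.41 in the two splits shown. These figures rest on linear weight loss, the assumed visit timing and dropout unrelated to outcome. The size for appetite is not established.

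This should be corrected before the final analysis. The documents do not show that LOCF must favour Treatment or that type I error is inflated at the planned, equal dropout rate.

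**What to change.** 1. Reconcile sections 8.1.2, 8.3 and 8.4 so that mITT has one definition throughout, including the Protocol Summary.
2. Make the main co-primary analysis one of all randomised subjects, by a mixed model for repeated measures or multiple imputation, and read the week-12 treatment contrast. For weight, use the measurements at weeks 1, 4, 8 and 12, which Appendix 6 already schedules. For appetite, use the diary weeks, once sections 8.1.4 and 9.8 agree on when diaries are completed.
3. Replace the one-at-a-time tipping point with delta-adjusted multiple imputation. Shift all missing week-12 values jointly over a stated grid, with separate shifts in Treatment and Control, and report where the conclusion changes. Both arms need shifting because heavier Control dropout is the split that favours Treatment in step 3.

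The cost is SAP wording and more programming; no extra weight measurements are needed. The downside is a missing-at-random assumption in the main analysis, which the delta grid then tests.

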
Visit Schedule
	
Screening/Baseline Visit 0 (-1 week; ± 7 days) – Obtain Informed Consent prior to any study procedures. Confirm subject has met all inclusion criteria and no exclusion criteria. History & Physical including height & weight, diet history, baseline clinical parameters, provide laboratory requisition, urine pregnancy test for women of childbearing potential (FOCBP), and questionnaires. Subjects will be given their first batch of paper diaries to complete to establish a baseline hunger.
 
Enrollment/Randomization Visit 1 (Day 0; ± 7 days) – Confirm subject continues to meet all inclusion criteria and no exclusion criteria. Assessment of T6/T7 dermatomes, clinical parameters, BP, weight, perform urine pregnancy test for FOCBP if not done at screening, administer TFEQ-R18V2 Questionnaire, assess for adverse events and changes to concomitant medications. Subjects will be randomized based on the blocked randomization algorithm.

Treatment and Control subjects will be instructed to follow a healthy diet and reduce calories, if possible, throughout the study and given the Diet Resources sheet in Appendix 18.11. They will also receive an electronic scale with instructions on use will be provided, and 8 copies of a daily paper diary will be provided. Subjects will be instructed to return with their paper diary(ies) at the next scheduled visit.

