Only the treatment subjects will receive a handheld smartphone with the custom application and an Elira wearable patch system. It is recommended for treatment subjects to utilize an TENS Clean-Cote Skin Wipes and/or alcohol prep pad wipe to maintain a clean application area for the treatment. Treatment subjects will also receive Cetaphil Moisturizing Lotion to be used nightly after removing the ELIRA patch and applied throughout the abdomen area. Subject will be instructed to notify site immediately if any irritation occurs. Treatment subjects will stimulate under the supervision of the investigator or coordinator for 30 minutes prior to being discharged with the device. Treatment subjects will be assessed for toleration of the stimulation to further evaluate dose adjustment. Treatment subjects will be discharged with the Elira wearable patch system & Smartphone App and instructions on use. Treatment subjects will be instructed to return with the Elira wearable patch system and smartphone app at their next scheduled visit. Completion of patient questionnaires (All subjects). A below the neck photograph of the Treatment subjects will be taken at the enrollment visit, with the subjects dressed in biker shorts and sports bra (F) or athletic shorts (M).

Therapy Phase Visits 2, 3, 4, 5, 6, and 7 (week 1, 4, 8, 12, 16, and 20, respectively; ± 7 days) – Treatment and Control subjects will be assessed for adverse events, changes to concomitant medications and commitment to exclusion criteria. Obtain BP and weight. Administer the TFEQ-R18V2 Questionnaire. Collect and review paper diaries, dispense new paper diaries and review instructions for weekly completion. All subjects will be encouraged to follow a healthy low-calorie diet throughout the study. At week 1, subjects will return their first week’s worth of paper diaries. At week 4, subjects will be given a new set of 8 paper diaries and instructed to complete paper diaries for each week beginning the day after the visit. At week 8, they will return their “week 4 diaries” and be given the next set of 8 paper diaries to be completed each week,....,until the final week of using the device (week 23-24).

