5. STUDY DESIGN

[figure not shown]
Randomized, adaptive parallel arm study. Subjects will be initially screened during a screening period (1 week, ± 7 days; Figure 2). During this screening period, prior to study procedures being performed, subjects will sign an informed consent form. Then they will have their weight and blood pressure measured, FOCBP will have a pregnancy test, get blood drawn for analysis (blood lipids, HbA1c), and complete patient preference questionnaires. At the end of the screening/baseline period, eligible subjects will be offered the chance to enroll in the study. After enrolling, subjects will be randomized to treatment or control groups.

The Treatment group will be instructed to follow a healthy diet that they will follow for the duration of the study and will receive training on the use of the paper diaries, electronic scale, smartphone app and the Elira wearable patch system. All treatment subjects will be required to stimulate in the office for up to 30minutes to confirm sufficient system training and to acknowledge understanding stimulation settings. A below neck photograph will be taken of the treatment group in requested attire (i.e. biker shorts and sports bra for women, biker shorts for men). Following this, subjects will enter the Therapy Period, for a ~24-week duration. Treatment subjects may be contacted by PI or clinical coordinator to address any questions related to device functionality or compliance. Device usage will be monitored throughout therapy phase to ensure proper functionality and subject safety.

The Control group will be instructed to follow a healthy diet that they will follow for the duration of the study and will receive training on the use of the weekly paper diary and electronic scale. The Control group will not receive the electronic smartphone app or the Elira wearable patch system/components.

At the end of the 3 months of the Therapy Period, all subjects will be assessed for weight loss, blood pressure, blood lipids, HbA1c, and will continue to participate through months 4-6 to confirm the long term safety of the device prior to being terminated from the study. A below neck photograph will also be taken at the 12 week visit.

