8.1.2 Analysis Populations

The intent to treat (ITT) analysis population is defined as all subjects who were enrolled.

The modified intent to treat (mITT) analysis population is defined as all subjects who initiated therapy (i.e., initiated their first Treatment Period Visit) and had data through week 12. All safety and effectiveness analyses will be completed on the mITT analysis population.

The per protocol (PP) analysis population is defined as all subjects who met all inclusion/exclusion criteria, completed all visits in the study without any major protocol deviations. All effectiveness analyses will be completed on the PP analysis population.

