9. STUDY PROCEDURES

The study is divided into four phases as defined below (See Appendix 66 for Schedule of Visits):

Study Phase	Definition
Screening Visit	Obtain Informed Consent. Completion of Pre-Study Survey. Determination of Inclusion and Exclusion criteria (including PHQ-9 questionnaire; Appendix 3), Medical History and Physical, Obtain Concomitant Medications, Weight Loss History, Blood Pressure, Height and Weight, Blood Tests (including a lipid panel, HbA1c, and Urine Pregnancy Test for FOCBP. Dispense and Instruct on completion of Weekly Diary.
Randomization / Enrollment Visit	
Confirm Inclusion/Exclusion criteria has been met, Weight, blood pressure, and AEs/Concomitant Medications assessed. Completion of baseline TFEQ-R18V2 (Appendix 4). Assessment of T6/T7 Dermatomes, UPT for FOCBP (if not done at screening). Completion of pre-enrollment photographs.
 
Randomization of subject. For both groups (control and treatment) train and dispense paper diaries and electronic scale, encourage low-calorie diet for duration of study, provide Diet Resources sheet (Appendix 18.11)
 
In Addition, For Treatment Group only, training) and assessment of use of smart phone app and Elira wearable patch system (Appendix 2); Initiation of therapy and dose adjustment. Provide TENS Clean-Cote Skin Wipes and/or Alcohol Prep Pads and Cetaphil Moisturizing Lotion with instructions on use, following a healthy low-calorie diet, as needed, dispense smart phone app and Elira wearable patch system. ELIRA Device training (Treatment Group). Paper VAS sheets

Therapy Period	
For Control and Treatment Groups: Confirm Inclusion/Exclusion criteria continues to be met, collect blood pressure, AEs, and review Adverse Device Events, paper diary (dispense additional diaries), weight, blood pressure, assess for AE's/concomitant medications, completion of hunger and Completion of TFEQ-R18V2, encourage continuation of low-calorie diet at each scheduled visit. Blood Tests taken at 12 weeks for lipids and HbA1c. Photographs will be taken at 12 weeks .
 
In Addition, For Treatment Group only: assess for Adverse Device Effects at each visit. Collect Elira wearable patch system and smart phone and download data, assess subjects use of electronic diary, completion paper sheets and stimulation sessions at each visit. Dispense smart phone app and Elira wearable patch system at each visit.

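### Section 8.4 starts the effectiveness mITT at an undefined first Treatment Period Visit, apparently Visit 2, so Treatment subjects who stimulate at Visit 1 and leave before Visit 2 are excluded

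*Combined protocol and SAP*

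**What the plan says.** The combined protocol and SAP defines the mITT population twice.

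- Section 8.4 uses "all subjects who initiated therapy, defined as subjects who initiated their first Treatment Period Visit" for the primary and secondary effectiveness analyses. It puts safety on the ITT population, meaning everyone enrolled.
- Section 8.1.2, repeated in the Statistical Analysis row of the Protocol Summary, uses "all subjects who initiated therapy (i.e., initiated their first Treatment Period Visit) and had data through week 12". It puts both safety and effectiveness on that set.

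Section 8.3 follows 8.1.2: it treats a week-12 visit as a condition of mITT membership.

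Therapy itself starts earlier. The phase table in section 9 lists "Initiation of therapy and dose adjustment" under the Randomization / Enrollment Visit, for the Treatment group. The Visit Schedule in the Protocol Summary says of the same visit: "Treatment subjects will stimulate under the supervision of the investigator or coordinator for 30 minutes prior to being discharged with the device". Section 5 agrees: "All treatment subjects will be required to stimulate in the office for up to 30minutes", after which subjects enter the Therapy Period.

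The therapy visits come later. The Visit Schedule lists "Therapy Phase Visits 2, 3, 4, 5, 6, and 7 (week 1, 4, 8, 12, 16, and 20, respectively" with a ±7-day window. The Study Outline and the Schedule of Events (Appendix 6) also begin the therapy columns at Visit 2.

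**The concern.** The rule is worded as a test of whether therapy began, but it tests attendance at a visit that appears to come about a week after therapy began. Take a Treatment subject who stimulates at Visit 1, has burning at the site on day 3 and withdraws on day 5. This subject has used the device, yet section 8.4 classes them as not having initiated therapy.

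Membership then depends on something that happens after randomisation. Sections 10.1.1 and 10.1.2 list burning, pain and skin irritation as risks of TENS. Control subjects get no device, so they cannot leave for that reason. If such exits occur, the Treatment arm loses the subjects least able to use the device, and the comparison no longer rests fully on randomisation.

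The point needs its own repair. Deleting the week-12 condition from 8.1.2, or letting 8.4 govern, would still leave these subjects out.

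**Working it through.** The plan states no figure on this point, so the check compares the definitions and then sizes the gap.

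**1. When therapy starts and which visit counts**

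| Item | Place in the documents | Timing |
|---|---|---|
| First stimulation, device taken home | Section 5; section 9 phase table; Visit Schedule, Visit 1 | Day 0 |
| First visit labelled therapy | Study Outline; Visit Schedule; Appendix 6 | Visit 2, week 1 ±7 days, so day 0 to day 14 |

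The gap is nominally 7 days and at most 14. No section calls Visit 1 a therapy or treatment visit.

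**2. What happens to a Treatment subject who stimulates at Visit 1 and leaves before Visit 2**

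| Governing text | Effectiveness | Safety |
|---|---|---|
| 8.1.2 and 8.3 | Out, by the week-12 condition; the visit clause adds nothing | Out, because safety is on the same week-12-restricted set |
| 8.4 | Out, by the visit clause alone | In, because safety is on ITT |

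The visit clause is decisive in one cell only: effectiveness under 8.4.

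**3. How many subjects**

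Inputs from section 8.2: 80 per group and 30% dropout. Assumption: dropout is spread over the 24-week Therapy Period.

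- Dropouts per arm: 80 × 0.30 = 24.
- Even loss: 24 / 24 weeks = 1 per week, so 1 by week 1 and 2 by day 14.
- Constant hazard: −ln(0.70)/24 = 0.0149 per week. By week 1, 80 × (1 − e^−0.0149) = 1.2; by week 2, 80 × (1 − e^−0.0297) = 2.3.

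This is about 1 to 2 subjects in each arm.

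**4. What that could do to the weight-loss estimate (illustration)**

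Inputs from section 8.2: 6% and 3.5% mean loss, SD 5%. Assumptions: these means apply to subjects who stay, early leavers have zero weight change, all 80 per arm are analysed, and the test is two-sided at 0.05 (the plan states no test level).

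- Equal loss of k per arm: difference = (6 − 3.5) × (80 − k)/80. For k = 1 it is 2.47 and for k = 2 it is 2.44, against 2.50.
- Loss in Treatment only: difference d = 6 × (80 − k)/80 − 3.5. With x = k/80, the Treatment variance is (1 − x) × 25 + x(1 − x) × 36, and s² is its average with 25. Power = Φ(d/(s√(2/80)) − 1.96).

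| k in Treatment only | Difference | Power |
|---|---|---|
| 0 | 2.50 | 0.885 |
| 2 | 2.35 | 0.843 |
| 4 | 2.20 | 0.791 |
| 8 | 1.90 | 0.665 |

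The rows for 4 and 8 show sensitivity only. Nothing in the documents supports those counts.

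**The case against.** The strongest reply is that this is a matter of terminology with little practical effect. It has four parts.

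- **The term is undefined.** Read together with the section 9 phase table, the first Treatment Period Visit might mean Visit 1. That is possible but unlikely. Under section 7.3 a subject is enrolled only once randomised, which happens at Visit 1, so on that reading the 8.4 mITT would almost equal ITT and the modification would exclude hardly anyone. Either reading calls for a definition.
- **The main analysis already excludes these subjects.** Sections 8.1.2 and 8.3 require week-12 data. This stands, and it confines the effect of the visit clause to 8.4.
- **Little outcome data is at stake.** Visit 2 brings the first scheduled clinic weight after Visit 1 and the first scheduled collection of paper diaries. A subject who never returns may have no collected baseline diary, so percent change in appetite may not be computable, and there is no later clinic weight to carry forward. This stands too. It is a reason to state the missing-data handling, not a reason to class the subject as never having started.
- **Unequal loss is not shown.** Section 10.1.2 expects adverse events at low frequency, the plan allows pauses in stimulation before withdrawal, and in an open-label trial Controls may leave early because they received no device. The direction and size of any imbalance are therefore unknown. What remains is that stimulation can act as a cause of exit in one arm only.

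**Conclusion.** The mismatch is real and narrow. Section 8.4 removes from its effectiveness set any Treatment subject who stimulated but did not reach the first Treatment Period Visit, and the schedules indicate that this is Visit 2. The identification with Visit 2 is an inference from visit labels. The expected number is about 1 per arm by week 1 and about 2 by day 14, if the plan's 30% dropout is spread evenly.

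A reader might infer three stronger conclusions that the documents do not support.

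- **That the visit clause changes the deciding analysis as 8.1.2 defines it.** It does not, since the week-12 condition does that work there.
- **That it inflates the safety success rate by about 1/80 = 1.25 points per lost subject.** Under 8.4 these subjects stay in for safety. The loss under 8.1.2 comes from placing safety on a week-12-restricted set, which conflicts with 8.4 and with the tabulation of discontinued subjects required in section 6.1.1 and the Protocol Summary endpoints.
- **That many Treatment subjects are lost to first-week intolerance.** For example, a quarter of the 24 dropouts would be 6 of 80. No early-intolerance rate is given, so such a figure is only an assumption.

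**What to change.** 1. In 8.1.2 and 8.4, and in the matching text of the Protocol Summary, define the main effectiveness set as all randomised subjects, counted from Visit 1 in both arms. This is in substance the ITT set already defined, and because it does not depend on stimulation it applies equally to Control.
2. Delete the week-12 data condition from 8.1.2. If only the visit clause is replaced, nobody is added under that section. Revise the remark in 8.3 that carrying values forward may not be needed.
3. State how subjects with no post-baseline weight or diary are handled, for example by including them through the missing-data method with a sensitivity analysis. Cover the case where the baseline diary was never collected.
4. State in 8.1.2 that safety is analysed from Visit 1 on all enrolled subjects, including everyone who received any stimulation, whether or not they return for Visit 2. This brings 8.1.2 into line with 8.4 and section 6.1.1.

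The cost is SAP wording and a few more subjects with imputed outcomes. The effect estimate may be slightly less favourable. No study procedure changes.
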